### 11.2 Safety, tolerability and palatability analyses

Reporting of the safety data will be of a descriptive nature and presented using appropriate summary statistics (e.g. n, mean, SD, %CV, median, minimum, maximum) or frequency

distributions (n%) by age group (age 1-11 years, age 12-< 21 years). Unless otherwise stated these tabulations will be supported by data listings.

Safety summaries will include all patients irrespective of whether or not they completed the trial.

AEs will be coded according to the current version of MedDRA (version to be identified in trial report).

Treatment emergent adverse events (TEAEs) will be determined and only these will be included in the statistical analysis report. Details of the criteria of classifying an AE as a TEAE will be provided in the Statistical Analysis Plan.

The incidence of adverse events will be summarised by system organ class, preferred term and maximum severity. Adverse events will also be summarised by strongest relationship to Investigational Medicinal Product by event and system organ class. If a patient experiences an adverse event more than once the event with the worst severity or at the most related to IMP occurrence will be considered. Patients will be included only once at each level where they experienced one or more events.

A summary of the incidence of serious adverse events will be presented by event and system organ class.

Adverse events relating to oro-pharyngeal tolerability data will be additionally listed separately and appropriately summarised.

All results for other safety will be appropriately summarised.

Palatability data will be appropriately summarised.

### **11.3 Data Safety Monitoring Committee (DSMC)**

An independent Data Safety Monitoring Committee will be formed to alert and/or make recommendations to The Sponsor about any existing or potential safety issues.

### **11.4 Reporting urgent safety measures**

If any urgent safety measures are taken the Investigator/Sponsor shall immediately and in any event no later than 3 days from the date the measures are taken, give written notice to the MHRA and the relevant REC of the measures taken and the circumstances giving rise to those measures.

Please refer to the following website for details on clinical trials safety reporting:

<http://www.mhra.gov.uk/Howweregulate/Medicines/Licensingofmedicines/Clinicaltrials/Safetyreporting-SUSARSandASRs/index.htm>

### **11.3 Statistical analysis**

#### **11.3.1 Analysis Populations**

The primary trial population will be the Pharmacokinetic (PK) population. The PK population will include those patients who had at least one successful blood sample taken and complete the trial without significant protocol deviations/violations which are likely to affect the determination of the pharmacokinetic parameters. Further details on what is deemed a significant protocol deviation/violation will be documented in the Statistical Analysis Plan. This population will be used for the analysis of the primary variable.

Safety data will be presented for the Safety population, that is, it will include all patients who received trial medication.

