## **3. TRIAL DESIGN**

### **3.1 Exit points**

The normal exit point from this trial will be when the patient completes the follow up of the second treatment period, i.e. when the patient returns to clinic for their next treatment course or for their next clinic review (it is anticipated that this will be approximately two to three weeks following 13-CRA treatment), all adverse events will be followed up to conclusion.

All patients who have at least one blood sample taken for the pharmacokinetic trial will be included in the population pharmacokinetic analysis. If the parent(s)/legal guardian or patient refuses further blood sampling the patient will be withdrawn from the trial.

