## **8 PREMATURE DISCONTINUATION FROM TRIAL**

### **8.1 Early Discontinuation of an Individual Patient**

Patients and their parent(s)/legal guardian will be informed that they have the right to withdraw from the trial at any time, without prejudice to their medical care and that they are not obliged to state their reasons. In addition, the investigator may remove a patient from the trial if, in the investigator's opinion, it is not in the best interest of the patient to continue in the trial.

Any withdrawal from the trial must be fully documented in the CRF and source.

The date of discontinuation from the trial and reason (where possible) for discontinuation will be recorded on the CRF and in the patient's medical records.

- Patients may be discontinued from the trial for the following reasons:
- Withdrawal of consent
- AE
- Deviation from protocol
- Other (to be specified on the CRF by the investigator if possible)

The data recorded (including PK samples) until the time of withdrawal will be used as part of the clinical trial unless the parent(s)/legal guardian or patient requests that it is not used.

Withdrawn patients may be replaced if the overall target number of samples has not been reached (i.e. a total of 150 samples).

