### **8.3 Patient and Trial Completion**

Patients will be considered to have completed the trial when the patient has completed the 14 day's follow up at the end of the My-CRA Month 2 dosing period. Patients who consent for the trial but who do not, for whatever reason, receive trial medication will be considered to be screening failures and their data will be recorded on a screening failure list. Patients who provide at least one pharmacokinetic blood sample for trial purposes will be deemed to have entered the trial and will be included in the PK analyses. All patients who receive trial medication will be considered for the safety analyses.

The trial will be considered to be completed 14 days after the last patient's has completed their My-CRA Month 2 dosing.

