## 11 EVALUATION OF RESULTS

Changes in the conduct of the trial or planned analyses will be reported in the corresponding section of the trial report.

A Statistical Analysis Plan (SAP) will be developed by a qualified statistician together with a pharmacokinetic modeller. Pharmacokinetic and Statistical analysis will be performed according to this document. The SAP will specifically include details of how all: Analysis Populations, Demographic and Baseline Characteristics, Completion and Discontinuation information, Medication details, Pharmacokinetic analyses as well as Safety analyses (including oropharyngeal tolerability) and Palatability will be classified and described. The SAP will be reviewed and approved prior to analysis.

The sample size chosen for the trial is considered appropriate based on previous experience. No formal sample size calculations have been performed. In order to develop a robust population pharmacokinetic model (i.e. precisely estimated parameters), data from a minimum of 150 blood samples will be required. It is hoped that the required number of samples may be obtained from 12-18 patients. However, if problems are encountered in obtaining samples further patients may be included in the trial. In order to accommodate these problems without having to submit repeated protocol amendments the protocol states up to 18 patients for inclusion in the trial.

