### 11.3.3 Data Analysis

Statistical analyses will be performed after all patients have ended their participation in the trial, protocol deviations reviewed, populations have been agreed and the database has been locked.

Details of this analysis will be included in the SAP.

Patients withdrawn before treatment administration will not be assessed for outcome variables or safety.

Continuous variables will be summarised using descriptive statistics; n, mean, standard deviation, %CV, median, minimum and maximum, while categorical variables will be summarised as the number (and percentage) of patients in each category.

Baseline and demographic data will be summarised overall and by age group (age 1-11 years, age 12-< 21 years) as appropriate.

Concomitant medications will be tabulated by age group along with the current available WHO drug dictionary coding by primary term and generic drug name.

As part of the pharmacokinetic analysis, statistical significance will be declared at the 5% level (two- sided). All other safety analyses will be simply summarised.

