9.1 Pharmacokinetic Population

The pharmacokinetic population will include those patients who had at least one successful blood sample taken and complete the trial without significant protocol deviations/violations which are likely to affect the determination of the pharmacokinetic parameters. This population will be used for the analysis of the primary variable.

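### Two rules decide who enters the primary PK analysis: one blood sample (Protocol 3.1, 8.3), or one sample plus trial completion without PK-relevant deviations (Protocol 11.3.1, SAP 9.1)

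*Protocol*

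**What the plan says.** Protocol 3.1 sets a one-sample rule for the model: "All patients who have at least one blood sample taken for the pharmacokinetic trial will be included in the population pharmacokinetic analysis". Its next sentence covers families who refuse further sampling and are then withdrawn, so leavers are plainly in view. Protocol 8.3 repeats the rule: patients with at least one PK sample "will be deemed to have entered the trial and will be included in the PK analyses". Protocol 8.1 defines no analysis set but points the same way: "The data recorded (including PK samples) until the time of withdrawal will be used as part of the clinical trial", unless the family or patient asks otherwise.

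Protocol 11.3.1 defines the PK population, which it makes the primary trial population, as "those patients who had at least one successful blood sample taken and complete the trial without significant protocol deviations/violations which are likely to affect" the PK parameters. SAP 9.1 repeats this and states: "This population will be used for the analysis of the primary variable". Protocol 8.3 gives the meaning of completion: patients are "considered to have completed the trial when the patient has completed the 14" days of follow-up after Month 2 dosing.

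On governance, Protocol 11 says of the SAP: "Pharmacokinetic and Statistical analysis will be performed according to this document". SAP sections 2 and 12, however, put the population PK analysis outside the SAP.

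**The concern.** The same analysis has two inclusion rules. Protocol 11.1 takes the primary PK parameters from the population model. Protocol 3.1 says that model includes everyone with a sample, while Protocol 11.3.1 assigns the primary variable to a set that also requires completion.

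The completion test has little to do with PK. It turns on a safety follow-up at which no PK blood is drawn. The planned mixed-effects model can use a patient with very few samples (Protocol 11.1), so dropping incomplete patients gives up information that the method was chosen to use. What is at stake is precision in CL/F and V/F and, in one type of case, a whole test-versus-reference comparison. There is also some room to choose the set once the data are known.

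**Working it through.** **Step 1. Apply each rule to three patients.** The third column reads completion in Protocol 11.3.1 only as a deviation filter. That is possible because SAP 8 lists missed evaluations as major deviations but excludes only for those thought likely to affect the PK parameters.

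| Patient | Protocol 3.1 and 8.3 | Protocol 11.3.1 and SAP 9.1, plain reading | Same, deviation-filter reading |
|---|---|---|---|
| (a) Withdraws after period 1 | In | Out | In, unless the missed visits are judged PK-relevant |
| (b) All four PK days, misses only the last follow-up | In | Out | In |
| (c) Completes, with a PK-relevant deviation | In | Out | Out |

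On the plain reading the rules disagree for all three. On the softer reading they still disagree for (c), because Protocol 3.1 and 8.3 contain no deviation exception.

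**Step 2. Timing.** Appendix I puts the last PK sample at Day 15/16 and the end-of-trial visit at Day 29, with no PK sample at that visit. Patient (b) has therefore given every planned sample before the visit that decides completion.

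**Step 3. Samples lost per patient.** There are four PK days, two per period. Assume 5 samples per PK day at age 2 or over, 3 under age 2, and no 24–48 h samples. These counts are soft: five is a minimum in Protocol 4.6 and a maximum in Appendix I, and three is a maximum.

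- Patient (a): 2 × 5 = 10 samples, or 2 × 3 = 6 under age 2.
- Patient (b): 4 × 5 = 20 samples, or 4 × 3 = 12 under age 2.

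**Step 4. Illustration for the whole trial.** Assume four patients under 2 and two patients aged 2 or over leaving after period 1. Both numbers are assumptions.

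- N = 12: planned 4 × (4 × 3 + 8 × 5) = 208. The one-sample rule keeps 208 − 20 = 188 and the completion rule keeps 208 − 40 = 168. Loss: 20/188 = 10.6%.
- N = 20: planned 4 × (4 × 3 + 16 × 5) = 368. The rules keep 348 and 328. Loss: 20/348 = 5.7%.

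All four retained totals exceed the 150 minimum in Protocol 5.

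**Step 5. Precision of relative bioavailability.** Patient (a) has data on one formulation and gives no within-patient comparison, so only patient (b) costs a pair. If the standard error varies as 1/√pairs, losing k of N pairs multiplies it by √(N/(N − k)):

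- 1 of 12: √(12/11) = 1.044, about 4%.
- 3 of 12: √(12/9) = 1.155, about 15%.
- 1 of 20: √(20/19) = 1.026, about 3%.

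This guide fits a simple paired comparison. It is not a calculation for the planned model.

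**The case against.** The strongest reply is that Protocol 3.1 is the more specific text for the model, so every sampled patient stays in it. SAP 9.1 then governs only the descriptive PK tables and figures. The SAP 17.3 listings of concentrations and parameters cover all patients, so nothing disappears from the report. Protocol 11.3.3 also requires "protocol deviations reviewed, populations have been agreed and the database has been locked" before analysis, and Protocol 13.6 has the sponsor settle evaluability beforehand. A separate modelling plan may exist that fixes the dataset.

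Part of this stands. The listings do retain the data, and the agreement step narrows the room for a data-driven choice. But no text says there are two datasets, one for the model and one for the tables. Agreeing populations fixes when the choice is made, not which definition applies. A modelling plan, if there is one, is not among these documents.

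Three stronger readings are tempting and not supported:

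- **A reader might infer that the model will be fitted to completers only.** Protocol 3.1 says otherwise; the defect is that the rules conflict.
- **A reader might infer that the 150-sample target is at risk.** Under the Step 4 assumptions with N held at 12, three leavers aged 2 or over would give 208 − 60 = 148 on the completion rule. But Protocol 8.1 allows replacement of withdrawn patients while the target is unmet, and Protocol 11 and SAP 7.1 allow further patients. At N = 12 there is room for 6 more under the cap of 18 in Protocol 11, or 8 under the cap of 20 elsewhere.
- **A reader might infer selection bias from tolerability-related withdrawal.** It is possible, but nothing in the documents shows such a link.

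**Conclusion.** The conflict is real and specific, and it concerns the set for the primary variable. It exists on either reading of Protocol 11.3.1. The plain reading also removes usable data: one period's concentrations from an early leaver, and a complete comparison from a patient who misses only the last visit.

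The size cannot be fixed, because the documents give no dropout rate and no power calculation. It is probably modest, at about 3% to 4% on the standard error for one lost pair under the rough guide. That loss arises only on the plain reading, since the deviation-filter reading keeps the patient who missed only follow-up. The sample-count percentages are illustrations resting on assumed leavers, an assumed age split and soft counts per PK day. The point merits correction because it is cheap to fix, not because a large effect has been shown.

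**What to change.** Reconcile all four places to one PK population: dosed patients with at least one evaluable post-dose sample, whether or not they complete the trial, subject to the opt-out in Protocol 8.1, and excluded only for PK-relevant deviations as in SAP 8.

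- Delete the completion condition from Protocol 11.3.1 and SAP 9.1.
- Add the deviation exception, or a cross-reference to it, to Protocol 3.1 and 8.3. Changing only the other two would leave patient (c) in conflict.
- State that this set serves both the population model and the SAP's PK tables and figures. Editing the SAP alone would not reach the model.
- State that the 150 samples are counted on this set, since Protocol 8.1 ties replacement to that total without saying whose samples count.
- If wanted, show a completers-only run as a sensitivity analysis.

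The cost is wording, with no new data. SAP 16 shows that the patients' ages were already known when it was written, so this is a late change to be documented in the reports under Protocol 11.3.5. The downside is that some patients in the main set will have data on only one formulation.

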### 11.3.2 Sample Size

Up to 20 patients, both male and female, aged 0 – < 21 years of age will be recruited.

There are no power calculations in this trial. The objective of this trial is to estimate the population pharmacokinetics of 13-CRA following the administration of 13-CRA liquid (test product) and extracted capsule (reference product). From a statistical point of view, the collected plasma 13-CRA concentration data are expected to relate to a non-linear, mixed effects model involving repeated measures. The developed pharmacokinetic model will estimate the parameters of the model and their associated within- and between-patient variability.

### 11.3.3 Data Analysis

Statistical analyses will be performed after all patients have ended their participation in the trial, protocol deviations reviewed, populations have been agreed and the database has been locked.

Details of this analysis will be included in the SAP.

Patients withdrawn before treatment administration will not be assessed for outcome variables or safety.

Continuous variables will be summarised using descriptive statistics; n, mean, standard deviation, %CV, median, minimum and maximum, while categorical variables will be summarised as the number (and percentage) of patients in each category.

Baseline and demographic data will be summarised overall and by age group (age 1-11 years, age 12-< 21 years) as appropriate.

Concomitant medications will be tabulated by age group along with the current available WHO drug dictionary coding by primary term and generic drug name.

As part of the pharmacokinetic analysis, statistical significance will be declared at the 5% level (two- sided). All other safety analyses will be simply summarised.

### 11.3.4 Missing, Unused or Spurious Data

The handling of missing, unused and spurious data will be described in the Statistical Analysis Plan.

### 11.3.5 Deviations from the Planned Statistical Analyses

Any changes to the planned analysis (as described in the protocol and Statistical Analysis Plan) will be documented in the statistical and clinical trial reports.

## 12 REGULATORY AND ETHICAL CONSIDERATIONS

### 12.1 Good Clinical Practice

The investigator and Sponsor will ensure that this trial will be performed in accordance with the protocol, the Declaration of Helsinki (9), and all applicable regulatory requirements. The trial will be conducted according to the protocol and to Standard Operating procedures (SOPs) that meet the guidelines laid down by the International Conference on Harmonisation (ICH) for Good Clinical Practice (GCP) in clinical trials. The Sponsor has implemented a quality management system to manage quality throughout all stages of the trial process, using a risk-based approach. A Study Management Plan will be developed and will include a risk analysis for identification, evaluation, control, communication, review and reporting of the risks to the safety and integrity of the patients and the scientific integrity of the trial. This risk analysis will identify processes and data that are critical to ensure human subject protection and reliability of results, this risk assessment will be reviewed as appropriate during the study.

## **12.2 Informed consent**

Before a patient can participate in the trial their parent(s)/legal guardian must give written informed consent to participation. Where applicable, the patient themselves will provide assent for the trial (generally in patients over 7 years of age). The informed consent process will be in accordance with ICH GCP, the Declaration of Helsinki and local regulatory requirements.

Patient information leaflets/informed consent forms will be based on master documents provided by the Sponsor and submitted and approved by the Independent Ethical Committee (IEC). Patient information leaflets will be designed to target specific age groups and levels of understanding in order to obtain patient assent for the trial as well as parental/legal guardian consent. The Sponsor must approve and retain copies of any changes requested by the IEC before the documents are used.

## **12.3 Regulatory authority approval**

Before the trial is initiated at a site the Sponsor will obtain approval to conduct the trial from the appropriate regulatory authority in accordance with any applicable country specific requirements. Regulatory authority approval for the clinical trial will be obtained prior to recruitment of patients into the trial and shipment of IMP.

## **12.4 Independent ethics committee requirements**

Before initiation of the trial at a given site written approval of the protocol, informed consent forms and patient information leaflets will be obtained from the appropriate independent ethics committee. If any amendments to any of these documents occur during the trial, written approval must be obtained prior to their implementation. The site will also apply to their Local Authority and IEC as appropriate for approval to participate in the trial. The principal investigator at each site is responsible for ensuring that these actions occur.

## **12.5 Data Safety Monitoring Committee (DSMC)**

Before initiation of the trial the final trial protocol will be supplied to the independent Data Safety Monitoring Committee who will make recommendations to The Sponsor about any existing or potential safety issues.

## **12.6 Indemnity and Insurance**

With respect to any liability directly or indirectly caused by the IMP in connection with this clinical trial the Sponsor assumes liability on behalf of the investigator for possible injury to the patient, provided the investigator has followed the instructions of the Sponsor in accordance with this protocol and any amendments thereto, that the IMP has been supplied by the Sponsor, and that the investigator has performed the clinical trial in accordance with scientific practice and currently acceptable techniques and knowledge. The Sponsor's liability is covered by liability insurance.

## **12.7 Patient Confidentiality**

The principal investigator must ensure that the patient's anonymity is maintained. On the CRFs or other documents submitted to the Sponsor, patients should not be identified by their names, but by their assigned identification number. If patient names are included on copies of documents submitted to the Sponsor, the names must be obliterated and replaced with the assigned trial patient numbers.

The principal investigator should keep a separate log of patient identification numbers, names, addresses, telephone numbers and hospital numbers (if applicable). Documents not for

submission to the Sponsor, such as signed informed consent forms, should be maintained in strict confidence by the principal investigator in the trial site file.

A screening failure log will be maintained for patients who have consented to participate in the trial but who, for whatever reason, are not eligible, withdrawn or decide to withdraw prior to taking part. This log will contain the following information:

- Patient trial number
- Patient initials
- Reason for trial withdrawal (if available)

CRF pages will not be completed for these patients.

The investigator shall permit authorised representatives of the Sponsor, regulatory authorities and IECs to review that portion of the patient's medical record that is directly related to the trial. As part of the required content of informed consent, the patient must be informed that his/her records will be reviewed in this manner. The Sponsor will have access to patients information on site during monitoring or auditing, no identifying information other than patient number will be transferred to the Sponsor.

